## Methods

The data is reported according to the RECORD guidelines (45) and is stored in the servers of Statistics Denmark, where the data will be analyzed.

Study population:

All people  $\geq 18$  years receiving a primary total hip arthroplasty in Denmark between 01.01.2010-31.12.2020 registered in DHR are included. Patients receiving a THA due to a hip tumor or metastasis are excluded, as well as patients with erroneous registration in DHR.

Exposure:

Surgery performed in an OR with LAF compared with surgery in an OR with TAF.

Follow-up:

Follow-up starts on the operation day and ends 365 days postoperatively. Follow-up is also ended at time of any revision, death or emigration.

Null hypothesis:

There is no difference in the risk of PJIs after a THA performed in a LAF OR as opposed to in a TAF OR.

Alternative hypothesis:

There is a lower or higher risk of PJIs after a THA performed in a LAF OR as opposed to in a TAF OR.

Endpoints:

*Primary endpoint:*

Revision due to infection, measured at t=90 days and t=365 days. Revision is defined as the first surgical intervention in the same hip after a primary THA with debridement, replacement, or removal of prosthetic parts.

A follow-up time of 90 and 365 days respectively is chosen, since 90 days is the recommended surveillance period in the United States and is traditionally the limit between early and late infections, whereas it is important to have a follow up of a year not to miss up to 20 % of the infections (46,47). At 1 year, 80-90 % of the surgically requiring infections that will occur in the lifetime of the hip prosthesis have taken place. After 1 year, the infection rate drastically decreases and is less likely to be due to contamination during surgery (30,47).

PJI is considered present when at least one of the following two criteria exists.

1. Two or more intraoperative deep-tissue samples of the same bacteria, isolated from at least three deep-tissue samples.
2. Deep infection is reported to DHR by the surgeon upon revision surgery.

The definition of PJI is based on the studies by Gundtoft et al. (30,31), where it has been concluded, that the validity of the PJI diagnosis is greatly improved when using these criteria, which are validated specifically for DHR. The original study by Gundtoft et al. used an extensive algorithm to determine if a PJI was present. However, there was no statistically significant difference between the extensive algorithm and a simplified algorithm, that defines a PJI as two or more positive identical bacterial samples (30).

The investigators definition is in line with international consensus (48) and does not differ greatly from the definition made by the European Bone and Joint Infection Society (EBJIS) (49), although erythrocyte sedimentation rate, aspiration of joint fluid, white blood cell count in joint fluid and histological examination of intraoperative tissue biopsies are not routinely used in Denmark. Thus, these criteria are not used. Sinus tract communication with the hip joint or an opening to the hip joint is expected to cause the surgeon to register the diagnosis “infection” in DHR upon revision. Data for this analysis will be extracted from DHR and

HAIBA. For the revision surgery to be registered in HAIBA, at least three biopsies at the revision surgery are required, hence this is a part of the criteria (50).

*Secondary endpoints:*

- 1) Revision registered as aseptic loosening in DHR.
- 2) Any revision registered in DHR.

Aseptic loosening is a separate endpoint, since it has been shown that aseptic loosening might in fact turn out to be a PJI and is thus a point of interest (32,51,52).

*Sensitivity analyses:*

In addition, the following sensitivity analyses will be made:

- a) Alternative outcome: Primary revision registered as PJI or with at least one positive biopsy of a bacterium.
- b) Alternative outcome: Primary revision reported to DHR with at least one positive biopsy of a bacterium AND the prescription of a relevant antibiotic, specified in appendix A.
- c) Analysis for the primary endpoint, but for data collected between 2017-2020, allowing for adjustment for BMI and ASA as possible confounders, as these variables are only registered in this period

A sensitivity analysis is made for a) and b), since Milandt et al. have shown that having one positive intraoperative bacterial culture increases the risk of an occult infection, that is later diagnosed upon re-revision. When there was only one unexpected positive culture (unexpected meaning not registered as PJI in DHR), first-time revisions were associated with an increased relative risk of 2.63 for subsequent re-revision specifically for PJI. However, this association was not observed for the patients with two or more unexpected positive cultures, which were much more likely to receive antibiotics and be treated as PJI, after the microbiology results were obtained. This is most likely, because one positive culture has been interpreted as contamination (32). A sensitivity analysis is made for c), since DHR only have ASA and BMI registered starting in 2017 and thus this cannot be adjusted for prior in the data prior to 2017.

EBJIS have proposed a term called PJI-likely which include 1 positive unexpected positive culture. PJI-likely is based on international consensus (48,49); however, the definition relies on analyses that are not commonly performed in routine practice in Denmark, as stated in the description of the primary endpoint. Since it is not possible to use these criteria in Danish register studies, the investigators have instead decided to do sensitivity analyses based on the validation of infections in the DHR by Gundtoft et al. (30) and the findings of Milandt et al. (32).

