## Variables

The investigators will look at several variables and adjust for these where needed. The variables obtained from DHR is body mass index (BMI), age, gender, time of surgery, diagnosis, type of prosthesis and fixation method, whether cement is used and if it contains antibiotics, previous operations on the same hip and ASA score. ASA score and BMI are only available from 2017 and onwards in DHR.

From NPR, concomitant diagnoses will be obtained to produce an Elixhauser comorbidity score, and socioeconomic factors, such as income and education will be obtained from the Danish Income Statistics Register and Education Register.

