#### Statistical analysis:

Descriptive results for continuous variables will be shown as mean(SD)/median(range) depending on the distribution of the variables. Categorical variables will be presented using frequencies and percentages. Persons operated in LAF and TAF ORs are compared using t-tests/Wilcoxon-tests and chi-square tests, respectively. This is supplemented with cumulative incidence plots showing risk of infection (primary outcome) for LAF and TAF, regarding revision due to other causes and death as competing events. The two groups are compared using Grays test. To fulfill the requirements at Statistics Denmark about data on individual persons, a smooth curve is used to make the plot rather than the statistical correct step-function. Information at time 90 and 365 days after the operation will be presented. This type of plot will be used for all endpoints.

For the primary endpoint, two Cox regression analyses will be performed with the time to PJI as outcome. One model will only cover the first 90 days of follow-up, the other will cover all 365 days of follow-up. Censoring is made at time of revision due to other causes than PJI, death, emigration, and end of follow-up (365 days after operation), whichever comes first. Bilateral THA will be included in the model as two observations with inclusion of a time-dependent variable conditioning on the status of the other hip (53). A robust sandwich covariance matrix estimate is used to account for the intrapersonal dependence.

The model will include the following potential confounders:

Education, age, comorbidities, gender, previous hip surgery, primary diagnosis, type of cement, type of fixation, year of surgery, income and duration of surgery. ASA and BMI will be adjusted for in sensitivity analysis c). A direct acyclic graph is used when determining the variables needed to adjust for.

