The linearity assumption for continuous confounders is checked by including these as cubic splines with 3 to 7 knots and using the model with lowest AIC, as suggested by Harrell (54). The proportional hazards assumption for the Cox-regression models is assessed using plots for the cumulative sum of martingale residuals. If the assumption is violated for the exposure (LAF/TAF), the time-axis will be split into smaller parts in which the assumption is fulfilled, and a separate Cox regression is made for each part. If the proportional hazard assumption is violated for confounders, time-dependent covariates is used for these.

Similar Cox-regression models will be used to analyze both secondary endpoints, as well as for the sensitivity analysis of the primary endpoint.

The assumptions of proportional hazards for these endpoints are checked as described for the model for the primary endpoint.

All tests will be two-sided and a p-value of  $<0.05$  will be considered statistically significant. Statistical analysis will be conducted using SAS version 9.4 (SAS Institute Inc.).

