### Missingness

Thanks to the Danish registers, there is no loss to follow-up for the primary and secondary endpoints, nor for the endpoints of the sensitivity analyses. Information for most of the confounders is based on mandatory registration in DHR, thus it is expected a very limited amount of missing data in the confounders (less than 5 % with missing information about one/several confounders). The missingness is not likely to be associated with the exposure, thus the complete case analysis is expected to be valid (55).

If the missingness is found to be more pronounced, multiple imputation will be used to create a full analysis data set. The imputation will use 100 samples. Multiple imputation will be made using R (The R Foundation). Results from analysis on the full analysis data set as well as for the complete case analysis will be presented.

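### Sensitivity analysis c) changes the calendar period and the covariate set together, so its result cannot be attributed to BMI and ASA without a 2017-2020 comparator on the primary covariates

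*Combined protocol and SAP*

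**What the plan says.** The study population (Methods) is primary THAs "between 01.01.2010-31.12.2020 registered in DHR are included". The Statistical analysis section lists 11 potential confounders for the primary Cox models: "Education, age, comorbidities, gender, previous hip surgery, primary diagnosis, type of cement, type of fixation, year of surgery, income and duration of surgery". BMI and ASA are not among them, because, as the Variables section explains, "ASA score and BMI are only available from 2017 and onwards in DHR".

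The list of sensitivity analyses then gives c): "Analysis for the primary endpoint, but for data collected between 2017-2020, allowing for adjustment for BMI and ASA as possible confounders". The Statistical analysis section adds that "ASA and BMI will be adjusted for in sensitivity analysis c". The reason offered is limited to data availability: "A sensitivity analysis is made for c), since DHR only have ASA and BMI registered starting in 2017". On the model, the plan says only: "Similar Cox-regression models will be used to analyze both secondary endpoints, as well as for the sensitivity analysis of the primary endpoint".

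Nowhere does the plan include a 2017-2020 model with the primary confounder set, an exposure-by-period term, or a rule for reading c) against the primary HR.

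**The concern.** Analysis c) is the only place where the plan adjusts for BMI and ASA. Since it is called a sensitivity analysis for the primary endpoint, readers will use it to judge whether leaving these two variables out of the primary model matters. The only planned HR for that purpose is the 2010-2020 HR, which differs from c) in three respects:

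- c) adds BMI and ASA.
- c) covers 4 of the 11 years. If the LAF effect differed between 2010-2016 and 2017-2020, the HRs would differ for that reason.
- c) is a smaller subset, so its HR departs from the full-cohort HR by chance.

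Adjusting for year of surgery lets baseline risk vary by year. It does not let the LAF HR vary by period, and it does not remove the subset's sampling variation. If patients lack BMI or ASA values, complete-case selection adds a further difference.

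The primary model already includes comorbidities, so the remaining BMI/ASA confounding may be modest, and a modest shift is what this comparison cannot show. A chance difference could be read as confounding, or a chance agreement as reassurance, in a study meant to inform hospital design.

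**Working it through.** The plan states no sample size, event count or power, so it has no figure to reproduce. The text settles the structural point; the arithmetic below only illustrates its size.

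**Inputs from the documents**
- Primary period 2010-2020: 11 years. Period of c) 2017-2020: 4 years.
- Registered one-year PJI incidence 0.57-0.80%, with true incidence about 40% higher (Rationale and background): 0.57 × 1.4 = 0.80% and 0.80 × 1.4 = 1.12%, or 800-1,120 events per 100,000 THAs.
- Up to 20% of infections would be missed without one-year follow-up (Endpoints).

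**Assumptions not in the documents**
- Even yearly volume.
- E = 1,000 events at 365 days, and 800 at 90 days (20% later).
- LAF share p of 50%, 80% or 90%.

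**Step 1. Precision of c).** With even volume c) holds 4/11 = 36% of the data. Its SE for the log HR is √(11/4) = 1.66 times the primary SE.

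**Step 2. Chance spread of the c)/primary ratio.** Take Var(full) = 1/(E·p·(1−p)) and Var(subset) = (11/4)·Var(full). Because the subset is nested in the full cohort, the variance of the difference in log HR is Var(subset) − Var(full). Hence SD = √(1.75/(E·p·(1−p))), and the 95% range of the ratio is exp(±1.96·SD). No confounding and no period effect are assumed.

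| Events E | LAF share p | SD | 95% range of ratio |
|---|---|---|---|
| 1,000 | 50% | 0.0837 | 0.85-1.18 |
| 1,000 | 80% | 0.1046 | 0.81-1.23 |
| 1,000 | 90% | 0.1394 | 0.76-1.31 |
| 800 | 50% | 0.0935 | 0.83-1.20 |
| 800 | 80% | 0.1169 | 0.80-1.26 |

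Over a wider assumed grid (7,000-11,000 THAs per year, incidence 0.57-1.12%, LAF share 50-90%) the range runs from 0.87-1.15 at its narrowest to 0.66-1.51 at its widest.

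**Step 3. The same-sample comparison.** The simulation used 2,000 runs per setting, 90,000 THAs, 1,000 events, a Poisson model as rare-event stand-in for Cox, two binary covariates (prevalence 20% and 10%, HR 2 each) and no period effect. With no imbalance between groups, the change in HR on adding the covariates to the same 2017-2020 patients had a 95% range of 0.990-1.010 at 50:50 and 0.987-1.013 at 80% LAF. The c)/primary ratio in the same runs spread over 0.846-1.186 and 0.830-1.220, close to Step 2.

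**Step 4. A modest true confounding effect.** Suppose a factor with HR 2 is present in 25% of one group and 20% of the other. The unadjusted HR is inflated by (1 + 0.25)/(1 + 0.20) = 1.25/1.20 = 1.042, so adjustment should multiply it by 0.96 (log −0.041). In simulation, c) against the primary HR pointed the wrong way in 29.9% of runs at 50:50 and 34.2% at 80% LAF. The normal approximation agrees: Φ(−0.041/0.0837) = 31% and Φ(−0.041/0.1046) = 35%. The same-sample comparison pointed the wrong way in under 0.1% of runs.

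**Step 5. If the LAF effect changed over time.** As a hypothetical, set log HR(primary) = (7/11)·early + (4/11)·late + BMI/ASA bias.

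| Early HR | Late HR | Bias | Primary | c) | c)/primary | Same-sample ratio |
|---|---|---|---|---|---|---|
| 1.2 | 1.0 | 1.0 | 1.123 | 1.000 | 0.890 | 1.000 |
| 0.9 | 1.1 | 1.0 | 0.968 | 1.100 | 1.136 | 1.000 |
| 1.0 | 1.2 | 1.136 | 1.214 | 1.200 | 0.989 | 0.880 |

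In the first two rows a period effect looks like confounding. In the third, confounding is hidden by an opposing period effect.

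**The case against.** The strongest reply is that the plan never says a difference between c) and the primary HR will be attributed to BMI and ASA. It says only that these variables can be adjusted for where they are recorded, and c) does that validly. This stands as a description of the text: the comparison is implied, not stated. But a stand-alone 2017-2020 estimate does not show whether the primary HR is confounded, and the plan offers nothing else to compare it with.

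Second, the wrong-direction rates of 30% and 34% belong to a small bias. A log shift of 0.041 is below one SE of the primary log HR (0.063 at 50:50 and 0.079 at 80% LAF, with 1,000 events). For a shift by a factor of 0.85 (log −0.163), the same SDs give Φ(−0.163/0.0837) = 3% and Φ(−0.163/0.1046) = 6%. The rule also scores only the sign of a difference and ignores the wider interval of c). All of this is fair: large confounding would usually show in the right direction. Modest confounding would not, and an interval for c) alone does not isolate the effect of adjustment.

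Third, nothing in the documents suggests that the LAF effect changed over time, and the event counts and LAF shares are assumed. Both points stand. The period examples show what could happen, not what did. The sampling-noise argument needs no period effect, and the structural gap needs none of the numbers.

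Finally, the remedy does not reach 2010-2016. That is correct and should be stated in the report.

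**Conclusion.** The concern holds. Analysis c) is a sound BMI/ASA-adjusted estimate for 2017-2020, but as planned neither agreement with the primary HR nor a difference from it can be assigned to BMI and ASA. The primary endpoint, model and estimate are unaffected; what is weakened is the plan's only check on confounding by these two variables.

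On size, chance alone would move the c)/primary ratio by roughly 15-20% either way at a 50:50 split, and by more with an unequal LAF share. This assumes about 800-1,000 events and even yearly volume. A same-sample comparison would vary by about 1% when there is no confounding, given the simulated covariates. The conclusion that the two changes are not separated rests on the text alone. The change should be made: it is inexpensive and replaces an ambiguous comparison with a direct one.

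**What to change.** In analysis c), at both 90 and 365 days, fit the Cox model twice on the same 2017-2020 patients: once with the primary confounder set, and once with BMI and ASA added. Report both HRs and the change between them. Base any statement about BMI/ASA confounding on that change, not on c) against the 2010-2020 HR.

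Use an identical analysis set for both fits: patients complete on all variables including BMI and ASA, and also the imputed data if the rule in the Missingness section applies ("If the missingness is found to be more pronounced, multiple imputation will be used to create a full analysis data set"). State that the result applies directly to 2017-2020 and carries over to 2010-2016 (7 of 11 years) only by assumption.

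The cost is one extra Cox model per time point, two in total, repeated on imputed data if imputation is triggered, plus two sentences in the plan. No new data are needed. The change does not measure BMI/ASA confounding in 2010-2016.

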#### Statistical analysis:

Descriptive results for continuous variables will be shown as mean(SD)/median(range) depending on the distribution of the variables. Categorical variables will be presented using frequencies and percentages. Persons operated in LAF and TAF ORs are compared using t-tests/Wilcoxon-tests and chi-square tests, respectively. This is supplemented with cumulative incidence plots showing risk of infection (primary outcome) for LAF and TAF, regarding revision due to other causes and death as competing events. The two groups are compared using Grays test. To fulfill the requirements at Statistics Denmark about data on individual persons, a smooth curve is used to make the plot rather than the statistical correct step-function. Information at time 90 and 365 days after the operation will be presented. This type of plot will be used for all endpoints.

For the primary endpoint, two Cox regression analyses will be performed with the time to PJI as outcome. One model will only cover the first 90 days of follow-up, the other will cover all 365 days of follow-up. Censoring is made at time of revision due to other causes than PJI, death, emigration, and end of follow-up (365 days after operation), whichever comes first. Bilateral THA will be included in the model as two observations with inclusion of a time-dependent variable conditioning on the status of the other hip (53). A robust sandwich covariance matrix estimate is used to account for the intrapersonal dependence.

The model will include the following potential confounders:

Education, age, comorbidities, gender, previous hip surgery, primary diagnosis, type of cement, type of fixation, year of surgery, income and duration of surgery. ASA and BMI will be adjusted for in sensitivity analysis c). A direct acyclic graph is used when determining the variables needed to adjust for.

The linearity assumption for continuous confounders is checked by including these as cubic splines with 3 to 7 knots and using the model with lowest AIC, as suggested by Harrell (54). The proportional hazards assumption for the Cox-regression models is assessed using plots for the cumulative sum of martingale residuals. If the assumption is violated for the exposure (LAF/TAF), the time-axis will be split into smaller parts in which the assumption is fulfilled, and a separate Cox regression is made for each part. If the proportional hazard assumption is violated for confounders, time-dependent covariates is used for these.

Similar Cox-regression models will be used to analyze both secondary endpoints, as well as for the sensitivity analysis of the primary endpoint.

The assumptions of proportional hazards for these endpoints are checked as described for the model for the primary endpoint.

All tests will be two-sided and a p-value of  $<0.05$  will be considered statistically significant. Statistical analysis will be conducted using SAS version 9.4 (SAS Institute Inc.).

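### Do two nested primary Cox models, at 90 and 365 days, need a rule for which one decides the single null hypothesis?

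*Combined protocol and SAP*

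**What the plan says.** Under Methods, the null hypothesis reads: "There is no difference in the risk of PJIs after a THA performed in a LAF OR as opposed to in a TAF OR". The alternative is its two-sided counterpart, and neither names a horizon. The primary endpoint, in the same section, does: "Revision due to infection, measured at t=90 days and t=365 days". The aim in the Abstract also names both horizons and ranks neither.

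The endpoint section gives a separate reason for each window. The shorter is chosen "since 90 days is the recommended surveillance period in the United States and is traditionally the limit between early and late infections". For the longer, the reason is that "it is important to have a follow up of a year not to miss up to 20 % of the infections".

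The Statistical analysis section then states: "For the primary endpoint, two Cox regression analyses will be performed with the time to PJI as outcome". It fits one model per window: "One model will only cover the first 90 days of follow-up, the other will cover all 365 days of follow-up". It adds that "All tests will be two-sided", with a significance threshold of 0.05. If hazards are not proportional for the ventilation comparison, "the time-axis will be split into smaller parts in which the assumption is fulfilled, and a separate Cox regression is made for each part". No order of testing, deciding window or multiplicity adjustment is given.

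**The concern.** One hypothesis with two tests, each at 5%, is the usual pattern of uncontrolled multiplicity. The tests are also nested, so agreement between them is not independent confirmation. If the two p-values split, the plan does not say whether the null has been rejected, and that reading could be chosen after the results are known.

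The stake would be the false-positive rate attached to a claim that laminar and turbulent airflow differ. The Perspectives section expects the result to help inform ventilation choices in hospital building, so a loosely read split result could carry weight.

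**Working it through.** The plan gives no sample size, power, event count or overall error rate, so there is no stated figure to reproduce. The check asks what error rate each possible reading implies.

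**Inputs**
- Level per test: 0.05 two-sided (Statistical analysis), so the critical value is c = 1.96.
- Two models, the 90-day window lying inside the 365-day window (Statistical analysis).
- f, the share of first-year infections that occur by day 90. This is not given. The endpoint section says a shorter follow-up may miss up to 20% of infections. As a share of first-year infections, that means f is at least 0.80. As a share of lifetime infections, with 80% to 90% of those occurring by one year (same section), f runs from (0.80 − 0.20)/0.80 = 0.75 to (0.90 − 0.20)/0.90 = 0.78. I take 0.75 to 0.90 as the working range; the 0.90 end is an assumption.

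**Formulas**

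Under the null, treat the two test statistics as bivariate normal with correlation √f, because the 90-day events are a fraction f of the 365-day events.
- Either suffices: 1 − P(|Z90| < 1.96 and |Z365| < 1.96)
- Both required: 0.05 + 0.05 − (either suffices)
- Split result: (either suffices) − (both required)

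**Results when there is no true difference**

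| f | √f | Either suffices | Both required | Split |
|---|---|---|---|---|
| 0.75 | 0.866 | 7.34% | 2.66% | 4.68% |
| 0.80 | 0.894 | 7.09% | 2.91% | 4.18% |
| 0.90 | 0.949 | 6.48% | 3.52% | 2.96% |

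A simulation of 4 million draws at f = 0.80 gave 7.10% and 2.92%. Two independent tests would give 1 − 0.95² = 9.75%, so the overlap keeps the inflation well below that. At f = 0.80, when one window is falsely significant the other is too in 2.91/5 = 58% of cases.

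**Setting the readings against the text**

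1. Two questions, one per horizon: each test stays at 5%. This fits the aim, the endpoint, the two justifications and the one-model-per-window plan.
2. One named window decides: that test stays at 5%. The text names none.
3. Either window suffices: about 6.5% to 7.3%. The plan states no such rule.
4. Both windows required: about 2.7% to 3.5%. The plan states no such rule, and its cost would be power, not false positives.

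The figures cover the two Cox models only. Gray's test and any time-split models are not counted.

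**The case for a change.** The strongest case for a change is that the plan chose a formal null, an alternative and a 0.05 threshold, so its decision rule should be complete. Split results are realistic. At f = 0.80, take an effect that is constant over the year. With 80% power at 365 days, 2.28% of studies would be significant at 90 days only and 11.54% at 365 days only, 13.8% in all. With 50% power the figures are 3.95% and 12.14%, 16.1% in all. Both power values are assumptions. One or two sentences, written now, would fix how such a result is read.

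It stands that the null is not written once per horizon and that no deciding window is named. It does not follow that the plan is defective:

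- Both estimates come from prespecified models, and results at both times are planned, so a reader would see a split.
- If a split arises because the effect changes over time, the proportional-hazards check and the time-split models address it. They do not address a split due to chance.
- Naming a deciding window is a trade-off. If 365 days decided, an effect confined to the first 90 days would lose its lone early signal in 11.5% to 12.1% of studies (same power assumptions, applied to the 90-day model). If 90 days decided, the same share would be lost under a constant effect. The endpoint section supports both windows and gives no ground for preferring one.
- Declaring two separate questions would be an adequate clarification, yet the chance of at least one false positive would remain about 7.1% at f = 0.80. A remedy that leaves the figure where it was shows that the figure does not measure a fault.

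**Conclusion.** No change to the plan is called for. The missing sentence is a drafting gap that an analyst fills sensibly from the rest of the text: two prespecified questions, each tested at 5%, which share the events of the first 90 days. Followed as written, the plan gives the same models, hazard ratios and confidence intervals under any of the readings.

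The largest effect in view is a rise from 5% to about 6.5% to 7.3% in the false-positive rate for the two models together. It requires someone to adopt an either-suffices rule that the plan does not contain. The range rests on 75% to 90% of first-year infections falling by day 90, which the documents imply only loosely, and on the bivariate normal approximation. Agreement between the two windows should not be presented as replication, since most events are common to both.
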